11.4. Subject Information

Baseline characteristics as recorded in the subject's original study, including demographics, medical and vaccination history will be summarized by cohort and original randomization (active vaccine versus placebo). Categorical variables will be summarized by frequency distribution (number and percentage of subjects) and continuous variables will be summarized by descriptive statistics (including mean, median, standard deviation).

11.5. Safety Analyses

The verbatim terms used in the CRF by investigators to document serious adverse events will be coded using the Medical Dictionary for Regulatory Activities (MedDRA). All serious adverse events will be included in the analysis. For each serious adverse event, the percentage of subjects who experience at least 1 occurrence of the given event and the number of events per person-year (where applicable) with corresponding 2-sided 95% confidence intervals will be provided, for each cohort and by original randomization (active vaccine versus placebo). In addition, these analyses will be provided by age group for Cohort 1.

The incidence of pregnancy, incidence of pregnancy outcomes (including spontaneous/elective abortion, intrauterine death/stillbirth, information on delivery) and incidence of live-born children will be summarized by original randomization (active vaccine versus placebo). Only pregnancies with estimated conception within 28 days after vaccination with MVA-BN-Filo or within 3 months after vaccination with Ad26.ZEBOV, and live-born children from these pregnancies, will be included.

Results for subjects who received active vaccine or placebo will be presented separately.

A summary for subjects who die or who discontinue due to a serious adverse event will be provided.

The use of medications taken in relation to serious adverse events will be summarized.

Additional summaries, listings, datasets, or subject narratives may be provided, as appropriate.

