The study will consist of an enrollment visit, a number of follow-up contacts and an end-of-study contact. These contacts are preferably conducted by phone; if not possible, a study site visit needs to be organized. Preferably, offspring from vaccinated female subjects will visit the study site for every study visit. If not possible, the child may be visited at home by study site staff or a qualified health care worker for data collection.

Data collection can start when a signed informed consent form (ICF) is available for the current study. Preferably, signing of the ICF occurs at the last visit of the subject's original study (or at birth for offspring). If this is not possible, baseline data will be collected when a signed ICF is available and data need to be captured retrospectively up to the moment of enrollment in the current study.

Data collection will be as follows for the 3 cohorts:

Cohort 1: Data for subjects vaccinated with Ad26.ZEBOV and/or MVA-BN-Filo (or placebo) in a Phase 1, 2 or 3 clinical study (adults, adolescents and children) and who consent to participation in the current study will be collected in 6-month intervals. Data collection will continue for a total of 60 months after prime vaccination (including the duration in the subject's original study).

Cohort 2: Data on the pregnancy outcome of female subjects who became pregnant with estimated conception within 28 days after vaccination with MVA-BN-Filo (or placebo) or within 3 months after vaccination with Ad26.ZEBOV (or placebo) in a Phase 1, 2 or 3 clinical study

and who consent to participation in the current study will be collected at notification of the pregnancy, and at the end of the pregnancy. These subjects will be followed in Cohort 2 up to the end of their pregnancy. Thereafter, female subjects will continue to be followed in Cohort 1 (to reach a total of 60 months follow-up after prime vaccination including the duration in the subject's original study); live-born children will be followed in Cohort 3.

Cohort 3: Data for children born to female subjects exposed to Ad26.ZEBOV and/or MVA-BN-Filo (or placebo) in a Phase 1, 2 or 3 clinical study who became pregnant with estimated conception within 28 days after vaccination with MVA-BN-Filo (or placebo) or within 3 months after vaccination with Ad26.ZEBOV (or placebo) and for whom consent for the current study is given will be collected in 6-month intervals and up to 60 months after birth.

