10.1. Completion

Cohort 1: Data for subjects vaccinated with Ad26.ZEBOV and/or MVA-BN-Filo (or placebo) in a Phase 1, 2 or 3 clinical study (adults, adolescents and children) and who consent to participation in the current study will be collected in 6-month intervals. Data collection will

continue for a total of 60 months after prime vaccination (including the duration in the subject's original study).

Cohort 2: Data on the pregnancy outcome of female subjects who became pregnant with estimated conception within 28 days after vaccination with MVA-BN-Filo (or placebo) or within 3 months after vaccination with Ad26.ZEBOV (or placebo) in a Phase 1, 2 or 3 clinical study and who consent to participation in the current study will be collected at notification of the pregnancy, and at the end of the pregnancy. These subjects will be followed in Cohort 2 up to the end of their pregnancy. Thereafter, female subjects will continue to be followed in Cohort 1 (to reach a total of 60 months follow-up after prime vaccination including the duration in the subject's original study); live-born children will be followed in Cohort 3.

Cohort 3: Data for children born to female subjects exposed to Ad26.ZEBOV and/or MVA-BN-Filo (or placebo) in a Phase 1, 2 or 3 clinical study who became pregnant with estimated conception within 28 days after vaccination with MVA-BN-Filo (or placebo) or within 3 months after vaccination with Ad26.ZEBOV (or placebo) and for whom consent for the current study is given will be collected in 6-month intervals, and up to 60 months after birth.

Refer to Section 10.2 for details on the withdrawal of subjects after unblinding of their original study.

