10.2. Withdrawal From the Study

A subject may be withdrawn from data collection in this study for any of the following reasons:

- Withdrawal of consent
- Lost to follow-up
- Death

After unblinding of their original study, subjects who received placebo will be withdrawn from further participation. This also applies to pregnant subjects who received placebo (ie, subjects enrolled in Cohort 2) or offspring from vaccinated female subjects who received placebo (ie, subjects enrolled in Cohort 3).

Subjects who are subsequently enrolled as a subject in another non-sponsor clinical study do not need to be withdrawn from the study. It is accepted that data collection in this study may be restricted by confidentiality agreement terms and/or conditions of another concurrent clinical study.

When a subject withdraws before completing the study, the reason for withdrawal is to be documented in the CRF and in the source documents.

If a subject is lost to follow-up, every reasonable effort must be made by the study-site personnel to contact the subject and determine the reason for withdrawal. The measures taken to follow up must be documented. In the event that the status of the subject cannot be determined and the

subject is considered to be lost to follow-up, an end-of-study form for the individual subject will be completed and a specific date for the last observation will be provided.

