11.7. Interim Analyses

There are no planned interim analyses. However, the accumulating data during study conduct may be used for reporting required for health authority submissions or other purposes. As this is a non-comparative study without formal hypotheses, any interim data may be used for purely administrative purposes without having an impact on study conduct or need for statistical

adjustments. All interim reporting must be approved by the study responsible physician and project statistician prior to conduct.

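### Section 11.5 tabulates the crude percentage of subjects with an SAE by active versus placebo, although placebo follow-up stops at unblinding and vaccine follow-up runs to 60 months

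*Protocol*

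**What the plan says.** Section 11.5 fixes two summaries for every SAE term: "the percentage of subjects who experience at least 1 occurrence of the given event and the number of events per person-year (where applicable". Both carry 2-sided 95% confidence intervals and are to be given "for each cohort and by original randomization (active vaccine versus placebo".

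The two groups are observed for different lengths of time by design:

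- **Vaccinated subjects, Cohort 1.** Section 3.1: "Data collection will continue for a total of 60 months after prime vaccination".
- **Offspring, Cohort 3.** Section 10.1: data "will be collected in 6-month intervals, and up to 60 months after birth".
- **Placebo subjects.** Section 10.2: "After unblinding of their original study, subjects who received placebo will be withdrawn from further participation". The same section applies this to "offspring from vaccinated female subjects who received placebo (ie, subjects enrolled in Cohort 3".

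The Full Analysis set in Section 11.3 requires only enrollment and one post-baseline visit. Nothing in Section 11 truncates vaccine follow-up at unblinding, sets a common window, or qualifies the percentage for unequal follow-up. Section 11.7 describes the study in these words: "As this is a non-comparative study without formal hypotheses".

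**The concern.** The percentage of subjects with at least one event is a cumulative quantity: it can only rise as follow-up lengthens. When one group is stopped early by rule and the other continues, the two percentages answer different questions. The placebo figure is the risk up to unblinding, and the vaccine figure is the risk up to 60 months. Set out by randomized group, they would show more SAEs on vaccine even if the vaccine had no effect.

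The person-year rate ordered in the same sentence is the natural protection, but it is incomplete. It is qualified by an applicability condition that is not defined. It also removes the bias only if the SAE rate does not change with time since vaccination or, in Cohort 3, with the child's age.

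At stake is how the main safety table reads. No test or decision rule uses the contrast. However, Section 2.2 says the data serve benefit-risk assessment, and Section 11.7 allows accumulating data to be used for health authority submissions. An apparent vaccine excess produced by length of follow-up is unwelcome in both.

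**Working it through.** The protocol states no SAE rate, unblinding date, loss rate or active:placebo split, so there is no figure of its own to reproduce. The direction of the bias follows from the follow-up rules. Its size needs assumptions, which are marked below.

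**Inputs from the protocol.** Vaccine follow-up is 60 months (5 years) after prime (Section 3.1). Placebo follow-up ends at parent-study unblinding (Section 10.2). Enrollment is up to about 3,000 (Section 11.2).

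**Assumed.** The SAE rate r is the same in both groups. Unblinding occurs at T = 1, 2, 3 or 4 years after prime. For the confidence intervals, the split is 2,250 vaccine to 750 placebo.

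**Step 1: constant rate, no loss.** P(T) = 1 − exp(−rT). With r = 0.01 per person-year, the vaccine percentage is P(5) = 1 − exp(−0.05) = 4.88%.

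| Placebo unblinded at | Placebo P(T) | Ratio P(5)/P(T) | Excess (percentage points) |
|---|---|---|---|
| 1 year | 1.00% | 4.90 | 3.9 |
| 2 years | 1.98% | 2.46 | 2.9 |
| 3 years | 2.96% | 1.65 | 1.9 |
| 4 years | 3.92% | 1.24 | 1.0 |

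The ratio is 1.00 only if unblinding comes at or after 60 months.

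**Step 2: sensitivity to the rate.** For unblinding at 2 years, the ratio is 2.50, 2.48, 2.46 and 2.39 at 0.1, 0.5, 1 and 3 per 100 person-years. The ratio hardly depends on the rate. The absolute excess does.

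**Step 3: sensitivity to loss.** With 10% annual loss in both groups, l = −ln(0.9) and P(T) = r/(r+l) × (1 − exp(−(r+l)T)). At r = 0.01, P(5) = 3.80%, and P(1), P(2), P(3), P(4) = 0.94%, 1.79%, 2.54%, 3.20%. The ratios are 4.02, 2.13, 1.50 and 1.19: smaller, but still above 1.

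**Step 4: would the intervals separate?** Clopper-Pearson 95% limits, expected counts as whole numbers:

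| Scenario | Vaccine | Placebo | Overlap? |
|---|---|---|---|
| 1 per 100, unblinded at 2 years | 110/2,250: 4.03–5.86% | 15/750: 1.12–3.28% | No |
| 1 per 100, unblinded at 3 years | 110/2,250: 4.03–5.86% | 22/750: 1.85–4.41% | Yes |
| 0.1 per 100 (one event term), unblinded at 2 years | 11/2,250: 0.24–0.87% | 1/750: 0.00–0.74% | Yes |

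**Step 5: does the person-year rate repair it?** Under a constant rate it does: both groups have rate r, ratio 1.00. Under a changing rate it does not. If the rate were 0.02 in year 1 and 0.01 afterwards in both groups, the average over 5 years is (0.02 + 4 × 0.01)/5 = 0.012, and over 2 years (0.02 + 0.01)/2 = 0.015. Equal risk then gives unequal rates, here lower on vaccine.

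**Step 6: equal windows.** With both groups cut at 2 years, each has an expected 1.98% at r = 0.01, ratio 1.00.

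**The case against.** The strongest reply is that the remedy already stands beside the problem: Section 11.5 orders person-year rates with intervals for the same groups. The applicability condition may be there only because person-years do not suit every pregnancy outcome. The study has no hypotheses and no testing, and calls itself non-comparative. Its SAE endpoints in Section 11.1 name exposed subjects and children from pregnancies soon after vaccination, and Section 11.5 says that active and placebo results are shown separately. Placebo subjects are present only because unblinding was delayed. Censoring rules and table layout normally belong in the SAP.

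The size can also be questioned. A 1-year cut-off is unlikely: placebo subjects enter around the end of their parent study and need a post-baseline contact, first scheduled at month 6, so the parent study would have to end by about 6 months after prime. For a single event term, the level at which Section 11.5 orders the percentage, the intervals overlap in the example above.

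Much of this stands. It limits the consequence to a misleading display and makes the later cut-offs the more relevant ones. It does not remove the defect. The protocol itself fixes both the measure and the grouping, and that pairing is biased under its own withdrawal rule. Showing the groups separately does not equalize their follow-up, and the person-year rate accompanies the percentage without correcting it.

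**Conclusion.** The concern holds. As written, Section 11.5 produces an active/placebo percentage that is expected to be higher on vaccine under equal risk whenever a parent study is unblinded before month 60. At an assumed 1 SAE per 100 person-years without loss, the expected ratio is 2.46, 1.65 or 1.24 for unblinding at 2, 3 or 4 years, an excess of 2.9, 1.9 or 1.0 percentage points. It would reach 4.90 in the unlikely case of unblinding at 1 year. Loss of 10% a year reduces these ratios without removing them. The size rests on assumed rates and dates; the direction does not.

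The defect concerns Cohort 1 and, by the same reasoning, Cohort 3, for which no separate calculation was made. In Cohort 2 follow-up ends with the pregnancy, so any difference is small. The 60-month percentage for vaccinated subjects is a legitimate estimate in its own right. The point should be fixed, but it does not threaten the study's objectives.

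**What to change.** Amend Section 11.5 as follows.

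1. Limit any active/placebo display of SAE percentages to follow-up before unblinding of each parent study, with both groups censored at that date. Alternatively, replace the crude percentage in that display with events per person-year by interval since prime (since birth for Cohort 3), or with Kaplan-Meier cumulative incidence at fixed times.
2. Report the 60-month percentage in a separate table for vaccinated subjects and their offspring only.
3. For SAEs in Cohorts 1 and 3, remove or define the applicability condition on person-year rates, so that a rate always accompanies the percentage.

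The cost is a change of wording and a few extra tables. The dates needed (vaccination, birth, unblinding, last contact) are required to define follow-up in any case. The drawback is that the concurrent display uses less vaccine person-time, so its intervals are wider. The 60-month table keeps the full vaccine data.

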Each local authority will determine which cohorts will be opened for enrollment in their region. It is not mandatory to open all cohorts for enrollment. As a result, a local authority may restrict enrollment to 1 or 2 cohorts, rather than allowing enrollment in all cohorts.

After unblinding of their original study, subjects from Cohort 1 and 2 who received placebo or offspring (Cohort 3) from female subjects who received placebo will be discontinued from further participation in this roll-over study.

SUBJECT POPULATION

The study will be open to subjects who participated in a Phase 1, 2 or 3 clinical study with Ad26.ZEBOV and/or MVA-BN-Filo and who received at least one dose of study vaccine (active vaccine or placebo).

SAFETY EVALUATIONS

Serious adverse event information in each cohort, pregnancy outcomes (including spontaneous/elective abortion, intrauterine death/stillbirth, information on delivery) and growth measurements for offspring will be collected.

STATISTICAL METHODS

There are no planned interim analyses. However, the accumulating data during study conduct may be used for reporting required for health authority submissions or other purposes. As this is a non-comparative study without formal hypotheses, any interim data may be used for purely administrative purposes without having an impact on study conduct or need for statistical adjustments. All interim reporting must be approved by the study responsible physician and project statistician prior to conduct.

No formal statistical testing of safety data is planned. Incidence rates of serious adverse events in each cohort, of pregnancy overall and by pregnancy outcome (including spontaneous/elective abortion, intrauterine death/stillbirth, information on delivery) will be calculated for all events and the number of events per person-year (where applicable), with corresponding 2-sided 95% confidence intervals. Incidence rates will also be tabulated by age group.

Results for subjects who received active vaccine or placebo will be presented separately.

TIME AND EVENTS SCHEDULE

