11. STATISTICAL METHODS

Statistical analysis will be performed by or under the authority of the sponsor. A general description of the statistical methods to be used to analyze the data collected in this study is outlined below. Specific details will be provided in the Statistical Analysis Plan.

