11.1. Endpoints

The following endpoints will be analyzed:

- Incidence of serious adverse events in subjects exposed to Ad26.ZEBOV and/or MVA-BN-Filo in a Phase 1, 2 or 3 clinical study, up to 60 months after prime vaccination.
- Incidence of pregnancy with estimated conception within 28 days after vaccination with MVA-BN-Filo or within 3 months after vaccination with Ad26.ZEBOV.
- Incidence of pregnancy by pregnancy outcome.
- Incidence of live-born children from a pregnancy with estimated conception within 28 days after vaccination with MVA-BN-Filo or within 3 months after vaccination with Ad26.ZEBOV.
- Incidence of serious adverse events in children born from a pregnancy with estimated conception within 28 days after vaccination with MVA-BN-Filo or within 3 months after vaccination with Ad26.ZEBOV up to 60 months after birth.

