11.2. Sample Size Determination

The enrollment projections of the contributing Phase 1, 2 and 3 clinical studies are estimated to result in enrollment of up to approximately 3,000 subjects.

The proposed study is based on analysis of prospective cohort data provided by investigators on subjects exposed to Ad26.ZEBOV and/or MVA-BN-Filo (or placebo). The study may include bias related to the observational nature of the data and potential lack of data due to loss to follow-up or essential data not collected routinely. Loss to follow-up may be pronounced in countries where infrastructure for data collection is lacking. Additionally, the study's ability to detect serious adverse events and the precision of these rates are based on the number of subjects participating in the study and completing study follow-up; however, this number is unknown.

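### Section 11.5 plans no follow-up-adjusted rate of subjects with an SAE: the by-arm percentage ignores unequal follow-up, and the only person-year measure counts repeat events

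*Protocol*

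**What the plan says.** Section 11.1 names the main endpoint as "Incidence of serious adverse events in subjects exposed to Ad26.ZEBOV and/or MVA-BN-Filo in a Phase 1, 2 or 3 clinical study, up to 60 months", counted from the first dose. It does not say whether incidence means a proportion of subjects, a first-event rate or an event rate.

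Section 11.5 plans two statistics for each SAE: "the percentage of subjects who experience at least 1 occurrence of the given event and the number of events per person-year". The second is qualified as applying only where applicable. Both come "with corresponding 2-sided 95% confidence intervals will be provided, for each cohort and by original randomization (active vaccine versus placebo"), and by age group for Cohort 1. The Synopsis (Statistical Methods) refers to incidence rates of SAEs in each cohort, which "will be calculated for all events and the number of events per person-year (where applicable), with corresponding 2-sided 95% confidence intervals".

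Neither place names a rate of subjects with a first SAE per person-year at risk, and neither names an interval method. Section 11 describes itself as general and adds: "Specific details will be provided in the Statistical Analysis Plan".

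Two other sections make follow-up unequal. Section 10.2 withdraws placebo recipients once their original study is unblinded, while vaccine recipients continue to 60 months. Section 11.2 warns that loss to follow-up may be pronounced in some countries.

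**The concern.** The endpoint counts affected subjects over a fixed horizon, but few placebo recipients may be observed to that horizon, and an unknown share of vaccine recipients will be lost before it. A percentage with all enrolled subjects in the denominator then mixes risk with length of observation. Set out by arm, it tends to show fewer placebo subjects with an SAE simply because they were watched for less time.

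A reader who sees this will turn to the person-year figure. That figure adjusts for follow-up, but it counts events rather than subjects. One subject with several hospitalizations over five years weighs as much as several subjects with one each. The plan has no measure that both adjusts for follow-up and counts each subject once.

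The study is descriptive, so no test is at risk. The estimates and their intervals are, however, its whole quantitative output.

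**Working it through.** The protocol gives no SAE rate, no distribution of repeat events, no interval formula and no power figure. Enrollment is "estimated to result in enrollment of up to approximately 3,000 subjects", which is a projection. There is no planned figure to reproduce. Every rate and clustering value below is an assumption, shown over a range.

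**1. Crude percentage under unequal follow-up.** With constant hazard h and follow-up t, the expected percentage is 1 − exp(−h·t).

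| h per person-year | 1 year | 2 years | 4 years |
|---|---|---|---|
| 0.01 | 1.0% | 2.0% | 3.9% |
| 0.02 | 2.0% | 3.9% | 7.7% |
| 0.05 | 4.9% | 9.5% | 18.1% |

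The hazard is the same along each row. At h = 0.02, the 4-year figure is 7.69/1.98 = 3.9 times the 1-year figure.

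A first-occurrence rate does not behave this way. Expected first events per subject are 1 − exp(−h·t), and expected person-years to first event or end of follow-up are (1 − exp(−h·t))/h. Their ratio is h for every t. At h = 0.02 this is 0.0198/0.990 = 0.02 after 1 year and 0.0769/3.844 = 0.02 after 4 years.

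**2. How far a few subjects can move the event rate.** Assume 3,000 subjects × 4 years = 12,000 person-years, with 60 subjects having 1 SAE each and 5 subjects having 8 each. That is 60 + 40 = 100 events in 65 subjects.

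- Event rate: 100/12,000 = 0.83 per 100 person-years.
- First-occurrence rate, taking first events on average 2 years into follow-up: 65/(12,000 − 65×2) = 65/11,870 = 0.55 per 100 person-years (exact 95% CI 0.42 to 0.70).
- Crude percentage: 65/3,000 = 2.2%.
- Without the 5 subjects, the event rate falls to 60/11,980 = 0.50. The first-occurrence rate falls only to 60/(11,980 − 120) = 0.51.

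**3. The interval on the event rate, if it were plain Poisson.** In the same example the exact Poisson 95% CI is 0.68 to 1.01 per 100 person-years. A subject-level robust CI is 0.57 to 1.22. The sum of squared counts is 60×1 + 5×64 = 380. Subtracting 100²/3,000 = 3.3 leaves 376.7, so the ratio of standard errors is √376.7/√100 = 1.94.

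More generally, gamma-Poisson counts were simulated for 3,000 subjects over 4 years (1,500 runs per setting). Here k is the variance of the between-subject frailty, and the variance inflation is 1 + k × mean events per subject. The table gives coverage of a nominal 95% exact Poisson interval on the total count.

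| SAEs per person-year | k = 0 | k = 2 | k = 5 | k = 10 | k = 20 |
|---|---|---|---|---|---|
| 0.005 | 96% | 96% | 96% | 94% | 91% |
| 0.02 | 95% | 93% | 91% | 86% | 79% |
| 0.05 | 96% | 91% | 84% | 75% | 62% |

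The robust interval covered 94% to 96% in every setting. At 0.02 and k = 20 the inflation is 1 + 20×0.08 = 2.6. At 0.005 and k = 5 it is 1 + 5×0.02 = 1.10. Because the inflation shrinks with the mean count, terms rarer than 0.005 per person-year are affected less still.

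**The case against.** The strongest reply is that both planned measures are ordinary safety summaries. The percentage is an incidence proportion, and events per person-year is an incidence rate that counts recurrences. The two are reported side by side, so a gap between them would reveal a few subjects with many events. Counting every SAE is a legitimate measure of burden, and a first-occurrence rate discards later events. Section 11.7 calls the study non-comparative, and Section 11.5 allows additional summaries. All of this stands. It rules out saying that neither planned statistic is an incidence measure, or that Sections 11.1 and 11.5 contradict each other.

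A reader might also infer that the planned intervals are too narrow. The documents do not support that. Section 11.5 specifies two-sided 95% intervals and nothing more, and the method is left to the SAP. A robust, bootstrap or negative binomial interval would fit the text. Section 11.5 also reports by individual SAE, where different SAEs in one subject fall under different terms and coverage stays near nominal for rare terms. The under-coverage bears mainly on pooled rates, which the Synopsis wording appears to include. Nothing in the protocol shows how often SAEs recur, and Section 1.1 describes the subjects enrolled so far as healthy adults.

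The reply does not remove the first problem. Putting the two measures side by side does not correct the percentage for follow-up, and the additional summaries are optional. Results are still tabulated by arm, and readers will compare the arms whatever the study is called.

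**Conclusion.** The point holds as a gap in the planned summaries that is cheap to close. Section 11.5 fixes a subject-based measure that ignores follow-up and a follow-up-adjusted measure that ignores who had the events. The distortion of the percentage follows from the protocol's own withdrawal rule and its own warning about loss. Its size depends on follow-up times and hazards that the protocol does not give. At an assumed 0.02 per person-year, the same risk reads as 2.0%, 3.9% or 7.7% after 1, 2 or 4 years.

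The sensitivity of the event rate to a few subjects is real in kind, but its size is assumed. The interval concern is conditional: it arises only if the SAP applies a plain Poisson interval to pooled SAEs that cluster within subjects. Coverage would then run from about 95% with no clustering to about 80% or lower with strong clustering, with little effect on rare single terms. It is a caution for the SAP and not an error in the protocol.

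The exact invariance of the first-occurrence rate to follow-up rests on a constant hazard and on follow-up ending for reasons unrelated to SAE risk. If the hazard changes over the 60 months, that rate also depends on the period observed, although it still counts each subject once and adjusts for time at risk.

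**What to change.** In Section 11.5, add the first-occurrence incidence rate: subjects with at least one occurrence, divided by person-years to first occurrence or end of follow-up, with a two-sided 95% CI. Give it for any SAE and by term, cohort and original randomization. Keep total events per person-year beside it, and state that its interval must allow for repeat events within a subject, for example by a robust variance or a subject-level bootstrap. The percentage of subjects can stay as a plain count summary.

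The event dates and end-of-study dates needed are already collected. The cost is one extra column and a sentence of text. The downside is that the event-rate intervals become somewhat wider than plain Poisson intervals where events cluster.
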